9.3 Efficacy and Safety Analyses

9.3.1 Disposition and Withdrawals

The number of subjects randomized, completing, and withdrawing, along with the reasons for withdrawal, will be tabulated. Additionally, the number of subjects in each analysis population will be reported.

9.3.2 Protocol Deviations

A by-subject listing of all protocol deviations will be reported.

9.3.3 Background and Demographic Characteristics

Baseline demographic variables will be summarized and presented by a subject listing. Demographic information will be presented for all analyses populations as defined in Section 9.2.

9.3.4 Concomitant Medications and Concomitant Therapies

Concomitant medications and therapies will be summarized by the number and percentage of subjects taking each medication, classified using World Health Organization Drug Dictionary (WHO-DD) Anatomical Therapeutic Chemical (ATC) class level 4 and preferred term. Concomitant medications will also be listed by subject.

9.3.5 Efficacy Analyses

9.3.5.1 Primary Efficacy Analysis

The primary efficacy endpoint and estimand are defined in Section 3.2.1.

PERMP-T scores at all post-dose time points (0.5, 1, 2, 4, 8, 10, 12, 13, and 14 hours post-dose) at visit 5 will be assessed using a linear MMRM analysis. This is a restricted maximum likelihood (REML)-based analysis implemented using SAS PROC MIXED. The model will include treatment, time and treatment by time as fixed effects and subject as a random effect. Pre-dose PERMP-T score will be included as a covariate. The difference between AMPH ER TAB and placebo will be assessed at the alpha = 0.05 level of significance. The covariance structure used in the final MMRM model will be the one that has the lowest Akaike Information Criterion (AIC) among the following selections: SP(POW), unstructured, compound symmetry (CS), heterogeneous CS or heterogeneous Toeplitz. Kenwood-Roger correction will be used to estimate denominator degrees of freedom. The treatment effect is estimated by the overall adjusted least square mean difference between two treatment groups. 95% CI for the adjusted least square mean will be constructed and p-value for the treatment comparison will also be provided.

The primary efficacy analysis will be conducted on the mITT population.

For the primary efficacy analysis, the MMRM model will be fit to the observed data with missing at random assumption. The rate of missing PERMP-T for at least one post-dose time point on will be calculated and summary (number and percentage) of subjects discontinued prior to Visit 5 by the

Confidential Page 50 of 67

dose level (5, 10, 15, 20 mg) prior to discontinuation will be summarized. Sensitivity analysis will be performed using Multiple Imputation approach with missing not at random assumption. In this analysis, the mean difference between the (unobserved) missing values and observed values (refer to as shift) will be assumed to vary independently for the different treatment groups. More details of this procedure will be provided in SAP.

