9.1 Power and Sample Size Determination

Assuming an effect size of 0.80 of the primary efficacy endpoint (PERMP-T score averaged over all post-dose time points assessed at Visit 5) between AMPH ER Tabs and placebo and approximately 92 completers, this study will have at least 93% power at the level of 0.05 (2-sided). To allow for an estimated 15% potential dropout rate, this study plans to enroll approximately 108 subjects to ensure that at least 92 complete. The study will be conducted in approximately 6 cohorts of 18 subjects because subjects will need to be enrolled in cohorts to facilitate the administration of serial PERMPs at Visits 5. An additional cohort of up to 18 subjects may be added to ensure at least 92 subjects complete the study if there are circumstances in which any of the cohorts are unable to enroll 18 subjects, or if the dropout rate is higher than expected (>15%) thereby having less than 92 completers to ensure sufficient statistical power.

The assumed effect size of 0.80 (expected treatment difference of 18 in average PERMP-T score divided by between-subject square root mean square error of 21.75) is based on differences measured between active and placebo in previous laboratory school studies conducted with similar drug formulations.

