9.3.5.2 Secondary Efficacy Analyses

Key secondary efficacy outcomes as determined by the comparison of each PERMP-T score at each time point (0.5, 1, 2, 4, 8, 10, 12, 13, and 14 hours post-dose) with pre-dose PERMP-T scores at Visit 5 are:

- Onset of clinical effect
- Duration of clinical effect

The key secondary variables of onset and duration of efficacy (clinical effect) of APMH ER TAB versus placebo using the comparison of each PERMP-T ((attempted + correct) score at each time point will be tested by the same method as the primary efficacy endpoint analyses implementing a linear MMRM model.

Onset of clinical effect is defined as the first time point post-dose when treatment effect is significant while the duration of clinical effect is defined as the time between last time point to the first time point post-dose with significant treatment effect.

The key secondary efficacy analysis will be conducted on the mITT population.

The key secondary efficacy endpoints (in the order of statistical analysis/gating) include:

• PERMP-T scores at 4, 2, 8, 10, 12, 1, 0.5, 13, and 14 hours post-dose

Descriptive statistics for the PERMP-T scores will be calculated at each time point and will be presented for each treatment as well for the differences between the treatments (AMPH ER TAB-placebo). In addition, these variables will be analyzed by the same method as the primary efficacy endpoint analyses implementing a linear MMRM model as described in Section 9.3.5.1 for the primary efficacy variable.

Additional secondary efficacy endpoints will include

- Change from Baseline in CGI-S at each post-baseline visit
- Change from Baseline in AISRS scores at each post-baseline visit
- Change from Baseline in DSST at Visit 5

Analysis of additional secondary endpoints will be performed for ITT population.

Descriptive statistics for the CGI-S, AISRS will be presented for each visit (Baseline and Visits 1 to 5). In addition, the change from Baseline in CGI-S, AISRS and DSST will be summarized.

For the AISRS, the proportion of responders (defined as a subject who has a change from Baseline 50% or greater in the AISRS) will also be presented.

Confidential Page 51 of 67

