9.3.7 Other Statistical Considerations

9.3.7.1 Significance Levels

The type I error significance level for each set of study analyses as applicable will be set at alpha = 0.05.

To preserve the family-wise error rate of 0.05, a gatekeeping testing procedure will be implemented for primary/secondary efficacy endpoints in the following order:

- PERMP-T scores over all post-dose time points assessed at Visit 5
- PERMP-T scores at 4, 2, 8, 10, 12, 1, 0.5, 13 and 14 hours post-dose

The above will test in sequence whether a significant treatment effect is present using the models previously specified. If a significant effect is noticed, the following test will then be examined until all endpoints are exhausted or failure to reject the null hypothesis is met at alpha = 0.05.

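### The MMRM fits one pre-dose PERMP-T slope for all nine post-dose times; if the true slope falls over the day, adding a pre-dose by time term would recover some precision at almost no cost

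*Combined protocol and SAP*

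**What the plan says.** Protocol section 9.3.5.1 gives the fixed and random effects: "The model will include treatment, time and treatment by time as fixed effects and subject as a random effect". The next sentence is the operative one here: "Pre-dose PERMP-T score will be included as a covariate". The synopsis and section 3.2.1 describe the same model, and none of the three lists an interaction of the pre-dose score with time. The covariance structure is the one with the lowest AIC among "SP(POW), unstructured, compound symmetry (CS), heterogeneous CS or heterogeneous Toeplitz". For the primary result, "The treatment effect is estimated by the overall adjusted least square mean difference between two treatment groups".

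Section 9.3.5.2 carries the model over to onset and duration: the time-point comparisons "will be tested by the same method as the primary efficacy endpoint analyses implementing a linear MMRM model". Section 9.3.7.1 tests them in fixed sequence after the primary: "PERMP-T scores at 4, 2, 8, 10, 12, 1, 0.5, 13 and 14 hours post-dose". Sections 9 and 9.3.5.1 leave detail to a SAP to be finalised before unblinding. The text reviewed contains no such detail on this term.

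**The concern.** A covariate entered only as a main effect has one regression slope. The post-dose scores run from 0.5 h to 14 h. If the pre-dose score is taken about 30 minutes before dosing (section 4.2.10.4 says so for Visit 4; I assume the same at Visit 5), the gap to the outcome grows from about 1 hour to about 14.5 hours. Serial scores often become less alike as the gap widens. If the slope falls with the correlation, a single value adjusts too little early and too much late.

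What is at stake is precision. Onset and duration are read from per-time significance, and the sequence stops at its first failure. The 8, 10 and 12 h tests stand third to fifth of the nine time-point tests, so a failure there blocks 1, 0.5, 13 and 14 h. A failure at 1 or 0.5 h blocks 13 and 14 h.

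**Working it through.** **1. The plan's own power figure.** Section 9.1 gives 92 completers, two-sided alpha 0.05 and an effect size of 0.80 (a difference of 18 over a root mean square error of 21.75). The allocation ratio is not stated; I assume 1:1, so n = 46 per arm. Power = Φ(d√(n/2) − 1.96).

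- d = 0.80: 0.80 × √23 = 3.837, Φ(1.877) = 97.0% (96.7% with the t distribution).
- d = 18/21.75 = 0.828: 3.969, Φ(2.009) = 97.8%.

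The stated figure of at least 93% holds as a lower bound but is not reproduced as a point value.

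**2. Formula for the loss.** With complete Visit 5 data and equal slopes in both arms, the common-slope estimate at time t is the difference in means at t minus b times the difference in pre-dose means. Time-specific slopes replace b by β_t. In large samples the variance with the common slope, relative to time-specific slopes, is

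- at time t: 1 + (β_t − b)² σ_X² / σ_t²
- for the day average: 1 + (β̄ − b)² σ_X² / 21.75²

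Here σ_X is the SD of the pre-dose score and σ_t the residual SD at t. Under compound symmetry (CS), b equals the mean slope β̄, so the day average loses nothing. Under an unstructured covariance (UN), the early times, with smaller residual variance, pull b above β̄.

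**3. Assumed inputs.** The documents give no hourly correlation, slope or SD. These scenarios are therefore assumptions, scaled so that the residual SD of the day average is 21.75. The first three hold the score variance constant, so slope equals correlation.

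| Scenario | Correlation 0.5 h → 14 h | Slope 0.5 h → 14 h | σ_X | σ at 0.5 h, 14 h | b: CS, UN |
|---|---|---|---|---|---|
| Mild | 0.88 → 0.77 | 0.88 → 0.77 | 52.3 | 24.6, 33.1 | 0.820, 0.852 |
| Moderate | 0.78 → 0.44 | 0.78 → 0.44 | 39.4 | 24.6, 35.3 | 0.575, 0.668 |
| Steep | 0.79 → 0.26 | 0.79 → 0.26 | 37.9 | 23.1, 36.6 | 0.472, 0.624 |
| SD rises 30% | 0.86 → 0.65 | 0.86 → 0.84 | 38.3 | 19.2, 37.9 | 0.840, 0.855 |

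**4. The moderate case in numbers.**

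- 0.5 h, CS: 1 + (0.78 − 0.575)² × 39.4²/24.6² = 1.108.
- 14 h, UN: 1 + (0.44 − 0.668)² × 39.4²/35.3² = 1.065.
- Day average, UN: 1 + (0.575 − 0.668)² × 39.4²/21.75² = 1.028. Power: Φ(3.969/√1.028 − 1.96) = 97.5%, down from 97.8%.

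**5. Variance ratios, all scenarios.**

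| Scenario | CS 0.5 h | CS 1 h | UN 8 h | UN 12 h | UN 14 h | Day average UN (CS = 1.00) | Primary power UN |
|---|---|---|---|---|---|---|---|
| Mild | 1.02 | 1.01 | 1.01 | 1.01 | 1.01 | 1.006 | 97.7% |
| Moderate | 1.11 | 1.07 | 1.03 | 1.06 | 1.07 | 1.028 | 97.5% |
| Steep | 1.27 | 1.17 | 1.08 | 1.12 | 1.14 | 1.070 | 97.0% |
| SD rises 30% | 1.00 | 1.00 | 1.00 | 1.00 | 1.00 | 1.001 | 97.8% |

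If the 14 h difference were 18 (assumed), the 14 h test under UN would lose 0.6, 2.7 and 5.6 points of power in the first three rows (74.2% to 73.6%, 68.5% to 65.8%, 65.5% to 59.9%).

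**6. Other assumption sets.** A second large-sample check with decaying correlations gave 1.02–1.10 at 8–12 h and 1.04–1.12 at 14 h under UN, and 1.04–1.22 at 0.5 h under CS. Simulation (46 per arm, UN, 3,000 runs per scenario, correlations from 0.82–0.91 at 0.5 h to 0.44–0.72 at 14 h) gave 1.02–1.05 for the day average and 1.02–1.09 at 14 h. SP(POW) behaves much like CS. Heterogeneous CS is the least favourable: in the steep case SE rises 10.0% at 14 h and 8.0% for the day average, leaving primary power at 95.7%.

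**7. Cost of the extra term if the slope is flat.** Estimating a separate slope at each time inflates variance by at most about 1/(N − 4) = 1/88 = 1.1%.

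**The case against.** The case for leaving the model alone is a fair one. A common-slope covariate is a legitimate prespecified choice. It raises no type I error or estimand problem and contradicts nothing else in the plan. Three stronger readings are tempting, and the documents support none of them.

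- A reader might infer that the pre-dose score is known to predict 0.5 h better than 14 h. No hourly PERMP-T data are given. Weaker prediction is also not the same as a smaller slope: correlation can fall because late scores are more spread out, and three of the five candidate structures (unstructured, heterogeneous CS, heterogeneous Toeplitz) allow for that. The last row of the tables is such a case, with almost no loss.
- A reader might infer that the primary and the late tests lose precision as a rule. With complete data the primary loses nothing under CS and about nothing under SP(POW). Under those two structures the early times lose more than the late ones. AIC chooses the structure, so which times would lose is not known in advance.
- A reader might infer that the testing sequence is endangered. The 14 h test stands last, so a failure there blocks nothing. At 8–12 h, where a failure would block later tests, the loss under UN is about 1–12% of variance in these scenarios, and the plan gives no hourly differences from which to work out the chance of failing.

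All of this stands. What remains is that the plan fixes the slope without giving a reason, and relaxing it costs almost nothing.

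**Conclusion.** The point holds as a minor, optional gain in efficiency. As written, the model has one pre-dose slope for all nine times, and the gated tests inherit it. If the slope declines over the day with roughly constant score variance, the variance loss is roughly 2–12% at 8–14 h under UN, or roughly 3–22% at 0.5–1 h under CS. The mild and steep scenarios above fall a little outside those ranges. The primary loses about 0–7% under CS or UN (more only in the steep case under heterogeneous CS), which is of little consequence at about 97% power. If the slope is flat, nothing is lost.

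The figures rest on assumed correlations, 1:1 allocation, complete Visit 5 data and equal slopes in the two arms. They describe true sampling variance, not the standard error that a misspecified structure would report. The treatment comparison stays unbiased by randomisation so long as the arms have the same expected pre-dose score. The pre-dose score is, in context, the Visit 5 score, taken after weeks of double-blind dosing, so that condition is itself an assumption. Whether it is the right covariate is a separate question; the present point applies to whichever score is kept.

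**What to change.** In section 9.3.5.1, and through it section 9.3.5.2, list the fixed effects as treatment, time, treatment × time, pre-dose PERMP-T and pre-dose PERMP-T × time, with LS means evaluated at the overall mean pre-dose score. Align the synopsis and section 3.2.1, and put the same model in the SAP before unblinding. If the sponsor prefers one slope, a sentence of justification in the SAP would do.

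The cost is one model term and eight extra parameters (nine slopes instead of one), or about 1% of variance if the slope does not change; study conduct is unaffected. A side benefit is that, with complete data, the point estimates then equal per-time ANCOVA whichever covariance structure AIC selects.

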9.3.5.2 Secondary Efficacy Analyses

Key secondary efficacy outcomes as determined by the comparison of each PERMP-T score at each time point (0.5, 1, 2, 4, 8, 10, 12, 13, and 14 hours post-dose) with pre-dose PERMP-T scores at Visit 5 are:

- Onset of clinical effect
- Duration of clinical effect

The key secondary variables of onset and duration of efficacy (clinical effect) of APMH ER TAB versus placebo using the comparison of each PERMP-T ((attempted + correct) score at each time point will be tested by the same method as the primary efficacy endpoint analyses implementing a linear MMRM model.

Onset of clinical effect is defined as the first time point post-dose when treatment effect is significant while the duration of clinical effect is defined as the time between last time point to the first time point post-dose with significant treatment effect.

The key secondary efficacy analysis will be conducted on the mITT population.

The key secondary efficacy endpoints (in the order of statistical analysis/gating) include:

• PERMP-T scores at 4, 2, 8, 10, 12, 1, 0.5, 13, and 14 hours post-dose

Descriptive statistics for the PERMP-T scores will be calculated at each time point and will be presented for each treatment as well for the differences between the treatments (AMPH ER TAB-placebo). In addition, these variables will be analyzed by the same method as the primary efficacy endpoint analyses implementing a linear MMRM model as described in Section 9.3.5.1 for the primary efficacy variable.

Additional secondary efficacy endpoints will include

- Change from Baseline in CGI-S at each post-baseline visit
- Change from Baseline in AISRS scores at each post-baseline visit
- Change from Baseline in DSST at Visit 5

Analysis of additional secondary endpoints will be performed for ITT population.

Descriptive statistics for the CGI-S, AISRS will be presented for each visit (Baseline and Visits 1 to 5). In addition, the change from Baseline in CGI-S, AISRS and DSST will be summarized.

For the AISRS, the proportion of responders (defined as a subject who has a change from Baseline 50% or greater in the AISRS) will also be presented.

Confidential Page 51 of 67

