3.3 Inclusion Criteria

Subjects must meet all of the following criteria to be considered eligible to participate in the study:

- 1. Male or female aged 18 to 60 years, inclusive at the time of Screening.
- 2. Diagnosed with ADHD using the DSM-5 criteria based on the Adults ADHD Clinical Diagnostic Scale (ACDS).
- 3. IQ within normal range based upon clinical opinion of the Investigator.
- 4. Baseline AISRS total score greater than or equal to 26.
- 5. Baseline score of 4 or higher in CGI-S.
- 6. Females who participate in this study will be of childbearing or non-childbearing potential:
 - Childbearing potential: Physically capable of becoming pregnant
 - Non-childbearing potential:
 - Permanently sterile (i.e., both ovaries removed, uterus removed, or bilateral tubal ligation for at least 6 weeks or documented successful hysteroscopic sterilization); and/or

Confidential Page 23 of 67

- Post-menopausal (no menstrual period for at least 12 consecutive months without any other medical cause).
- 7. Females of childbearing potential must be non-lactating and must have a negative serum pregnancy test at Screening.
- 8. Willing to use acceptable, effective methods of contraception.
- 9. Be able to attend the clinic regularly and reliably.
- 10. Be able to understand, read, write, and speak English fluently to complete the study-related materials.
- 11. Be informed of the nature of the study and give written consent prior to any study procedure.

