9 STATISTICAL CONSIDERATIONS

This is a phase 3 randomized, double-blind (DB), placebo-controlled, parallel, study to assess the efficacy and safety of AMPH ER TAB compared to placebo for the treatment of ADHD in adults aged 18 to 60 years. The objective of the statistical analysis will be to evaluate the efficacy and safety of AMPH ER TAB compared to placebo in adult patients with ADHD aged 18 to 60 years.

All continuous study assessments will be summarized by treatment and time point using descriptive statistics (n, mean, median, standard deviation, minimum, and maximum). All categorical study assessments will be summarized by treatment and time point using frequency counts and percentages. Hypothesis testing, unless otherwise indicated, will be two-sided and performed at the 0.05 significance level.

A detailed statistical analysis plan (SAP) will be written and finalized prior to unblinding of the data.

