9.2 Analysis Populations

The analysis populations are defined as follows:

- **Safety Population (SAF)**: The safety population is defined as all enrolled subjects who received at least one dose of study drug, with treatment assignment based on the actual treatment received.
- Randomized Population (RAND): The randomized population is defined as all randomized subjects, with treatment assignment based on the randomized treatment (regardless of actual treatment received).
- Intent-To-Treat Population (ITT): The ITT population is defined as all randomized subjects who received at least one dose of study drug treatment, with treatment assignment based on the randomized treatment (regardless of actual treatment received).
- **Modified Intent-To-Treat Population (mITT)**: The mITT population is defined as all subjects who are in the ITT population and have at least one PERMP-T score at Visit 5.

The primary efficacy analysis and key secondary efficacy analysis will be performed on the mITT population. Analysis of additional secondary endpoints will be performed for ITT population.

Confidential Page 49 of 67

The safety analyses will be performed on the safety populations.

Deviations from the original statistical plan as planned in this protocol will be reported and justified in the SAP and clinical study report (CSR) as appropriate.

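### AISRS, CGI-S and DSST are secondary efficacy endpoints, but the plan only summarises them by arm: no pre-specified baseline-adjusted drug-placebo estimate or confidence interval, and no joint model of the AISRS and CGI-S visits.

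*Combined protocol and SAP*

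**What the plan says.** The efficacy objective (Section 2.1) is comparative, drug against placebo. Sections 3.2.2 and 9.3.5.2 list three additional secondary outcomes: "Change from Baseline in AISRS scores at each post-baseline visit", "Change from Baseline in CGI-S at each post-baseline visit" and "Change from Baseline in DSST at Visit 5". Section 9.2 sets the population: "Analysis of additional secondary endpoints will be performed for ITT population".

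The analysis itself is short. Section 9.3.5.2 gives by-visit descriptive statistics for CGI-S and AISRS and an AISRS responder proportion, and for the change scores says: "In addition, the change from Baseline in CGI-S, AISRS and DSST will be summarized". The general rule at the head of Section 9 fills in what that means: "All continuous study assessments will be summarized by treatment and time point using descriptive statistics", namely n, mean, median, SD, minimum and maximum.

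The missing-data text (Sections 9.3.5.1 and 9.3.7.2) concerns PERMP only. At Early Termination, AISRS, CGI-S and DSST are optional (Section 4.2.10.6; Appendix A makes them conditional on the investigator's request). Section 9.3.8 analyses data under the visit recorded in the eCRF.

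**The concern.** Within one section, PERMP-T receives between-arm differences and an MMRM adjusted for the pre-dose score, while the symptom scales receive neither. The Baseline score is collected for all three scales. AISRS and CGI-S are measured at five post-baseline visits, and Appendix C records regulator feedback asking for CGI-S at several time points to assess improvement.

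Three things are lost:

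- A pre-specified treatment estimate with an interval. Any between-arm figure in the report would be chosen after the protocol was written, with the method left open.
- The link between visits. A subject who attends Visits 1 to 3 and then leaves appears in those three tables, but the earlier scores do nothing to inform the Visit 5 comparison.
- Clarity about who is in the Visit 5 table. The label is ITT, but the content is whoever was assessed at that visit.

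The second point matters more here because the primary and key secondary analyses use the mITT population, which requires a PERMP-T score at Visit 5. AISRS and CGI-S are the efficacy measures that could bring early leavers into a longitudinal comparison.

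**Working it through.** **1. How many subjects the Visit 5 summaries cover.** Inputs from Section 9.1: 108 enrolled, 15% dropout, 92 completers.

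- 108 × 0.85 = 91.8, which reproduces the plan's figure of about 92.
- 108 − 92 = 16 subjects without a Visit 5 assessment, and 16/108 = 14.8%.

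Early Termination values do not close this gap as written: they are optional, and no rule assigns them to Visit 5.

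**2. What is specified for each endpoint.**

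| | PERMP-T | AISRS, CGI-S | DSST |
|---|---|---|---|
| Post-baseline or post-dose measurements | 9 times at Visit 5 | Visits 1 to 5 | Visit 5 only |
| Between-arm difference | yes | none named | none named |
| Baseline or pre-dose covariate | yes | none named | none named |
| Model | MMRM | none named | none named |
| Missing-data approach | stated | none | none |

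With one scheduled post-baseline value, DSST has no repeated visits to model. The joint-model point concerns AISRS and CGI-S only.

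**3. What baseline adjustment is worth.** The documents give no SD, effect size or correlation for these scales, so everything here is assumed. Let r be the baseline to follow-up correlation and k the baseline SD divided by the follow-up SD, with follow-up variance set to 1.

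- Variance of a change score: 1 + k² − 2rk
- Residual variance after baseline adjustment: 1 − r²
- The first minus the second is (k − r)², so on these formulas adjustment never does worse, and gains nothing when k = r.
- Narrowing of the interval: 1 − √[(1 − r²)/(1 + k² − 2rk)]

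The narrowing does not depend on sample size, so the unstated allocation ratio does not matter.

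| r | k = 1: change, adjusted | narrower by | k = 0.6: change, adjusted | narrower by |
|---|---|---|---|---|
| 0.2 | 1.60, 0.96 | 22.5% | 1.12, 0.96 | 7.4% |
| 0.4 | 1.20, 0.84 | 16.3% | 0.88, 0.84 | 2.3% |
| 0.6 | 0.80, 0.64 | 10.6% | 0.64, 0.64 | 0% |

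At k = 0.8 and r = 0.4 the variances are 1.00 and 0.84, a gain of about 8%. Values of k below 1 are plausible because entry criteria set a floor on the Baseline AISRS and CGI-S scores.

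**4. Does the Visit 5 gap bias the comparison?** The documents give neither direction nor size. A simulation under assumed values does not show a large effect. It used unit SD, a 0.5 SD true effect, visit correlations either decaying as 0.85 per visit or constant at 0.6, and dropout of 10% to 20% per arm, either unrelated to the current score or rising with it. In ten scenarios the completers' difference in change lay within 0.010 SD of the all-subject difference. These scenarios let dropout depend only on the current score, so they do not rule out bias under other mechanisms.

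**The case against.** The strongest reply is that these are third-tier endpoints outside the gatekeeping sequence of Section 9.3.7.1. The objective is tested through the PERMP-T primary and nine gated time points, and Appendix C quotes the regulator as accepting the PERMP. Describing lower-tier endpoints is a legitimate choice, and a modelled result would still be nominal. This stands. It limits the weight of the point but does not supply the missing estimate.

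The plan also promises a detailed SAP before unblinding, and that document is not available here. A model may have been added. But Section 9.3.5.1 expressly leaves the imputation details to the SAP, while Section 9.3.5.2 makes no such deferral for these scales and states a descriptive method instead.

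Withdrawing subjects are encouraged to complete the final visit (Section 3.6), and Visits 1 to 4 include everyone still attending. So the coverage concern is confined to Visit 5, and 16 missing is a planning figure.

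Three stronger readings are tempting, and the documents do not support them:

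- A reader might infer that the trial cannot state a drug-placebo difference on symptoms at all. It can: n, mean and SD by arm give a crude unadjusted difference and interval.
- A reader might infer that the entry floor ("Baseline AISRS total score greater than or equal to 26", with CGI-S of at least 4) invalidates the comparison through regression to the mean. Both randomised arms meet the same floor, so the effect inflates change within each arm and is expected to cancel between them.
- A reader might take the 23% to 11% gains as the expected benefit. They require equal variances, which the entry floor makes doubtful for AISRS and CGI-S.

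**Conclusion.** The point holds as a gap in specification. For three named secondary efficacy endpoints under a comparative objective, the plan yields descriptive summaries by arm and no pre-specified, baseline-adjusted treatment estimate or interval. AISRS and CGI-S visits are not modelled jointly, and the Visit 5 summaries would rest on about 92 of 108 subjects if dropout is 15%.

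The precision at stake, relative to an unadjusted comparison of change scores, runs from nothing to about 23% of interval width over the values tried (r of 0.2 to 0.6, k of 0.6 or 1, all assumed). No bias in the drug-placebo difference has been shown. The primary analysis, its power and the gated tests are untouched. This is an inexpensive improvement the sponsor should make, and it leaves the trial's main conclusion as it is.

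**What to change.** In Section 9.3.5.2, and in the SAP before unblinding:

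- AISRS and CGI-S: analyse change from Baseline in the ITT population with an MMRM using all post-baseline visits. Terms: treatment, visit, treatment by visit, baseline score, and baseline by visit. Name the covariance structure in advance.
- DSST: analyse change at Visit 5 by ANCOVA with treatment and Baseline DSST.
- Report least squares mean differences with 95% CIs, labelled nominal and outside the PERMP-T gatekeeping sequence. Keep the descriptive tables, with n at each visit.
- State how Early Termination values of these scales enter the analysis.

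The cost is a few lines of text and standard programming on data already scheduled for collection. Section 9.2 asks for departures from the protocol's statistical plan to be reported and justified, so the change should be recorded that way. There are two drawbacks. The p-values will not be controlled for multiplicity. The MMRM also assumes data are missing at random, and it cannot recover subjects with no post-baseline score. The DSST analysis will still rest on those with a value assigned to Visit 5.
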